3.6 Timing of outcome assessment

Screening window is 0–28-days followed immediately by Baseline 1 assessments. Initial dose of treatment occurs at baseline appointment but after baseline visit outcome assessments have occurred. Baseline 1 treatment window is 42 days +/- 3 days and then End of Treatment visit 1 assessments occur. The final dose of treatment occurs at the beginning of treatment visit prior to End of Treatment 1 outcome assessments. Then a 42 day +/- 3 days washout. Baseline 2 treatment window is 42 days +/- 3 days and then End of Treatment visit 2 assessments occur. The final dose of treatment occurs at the end of treatment visit 2 prior to outcome assessments.

Section 4: Statistical Principles

The trial has a 2-stage design:

In Stage 1 the trial will compare three dosing schedules of 72 IU intranasal oxytocin (daily, alternate day, or every 3rd day dosing) for patients with FTD compared to placebo. Twenty participants per arm will be randomized to each of the three dose arms and order of the cross-over (order of oxytocin and placebo). All dose schedules will use sprays bid (morning and afternoon, with placebo on non-oxytocin Rx days) to maintain blinding to schedule across all of the cohorts. After 6 weeks, patients will have a 6-week washout period and then cross-over to the other treatment arm (placebo to oxytocin; oxytocin to placebo). After 60 participants have completed their participation, interim Bayesian analysis will determine which of the dosing schedules appears most promising. For Stage 2, the most promising dose schedule, designated the “target dose,” will be carried forward for the remainder of participants n=40 who will complete the exact same procedures as participants in Stage 1. Data from the target dose group from stage 1 and 2 will be combined for the final analysis.

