4.1 Confidence Intervals and P-values

Stage 1 and Stage 2 for the target selected treatment arm will be used to test superiority using a nominal 2.5% one-sided test for the primary outcome of change in NPI.

All secondary, safety and exploratory outcomes will be reported as two-sided tests with statistical significance set at a two-sided 0.05 level.

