6.2 Analysis Methods

The primary analysis of the change from baseline NPI apathy domain is based on a linear model with covariates for sex and order of treatment in the crossover including data from both Stage 1 and Stage 2 for the target selected treatment arm (ETD) will be used to demonstrate superiority using a nominal 2.5% one-sided test using the PPP. Estimated mean effect of the treatment compared to placebo and 95% confidence intervals will be reported. Analysis will compare relative period effects for PBO and OXY periods via change in scores from Baseline to End of Treatment visit.

Supportive primary analysis will be conducted on the MITT population. Given the crossover design, the ITT analysis excludes those that did not take any study medications in their second treatment period.

Sensitivity analysis combining all dose groups for OXY vs. PBO will be conducted for all primary, secondary, and exploratory outcome measures.

Covariates:

Order of treatment (End of treatment 2: Oxytocin versus End of Treatment 2: Placebo)

Sex (male vs female)

Subgroup analyses:

By sex

By severity

Age (median split : young <67 years; older 67+ years)

Oxytocin Genetic polymorphism (GG vs AG vs AA)

FTD subtype (bvFTD vs PNFA vs SD)

ALL other outcomes as listed above, will be analysed using the same methods as for the primary outcome using 5% 2-sided test. Subject is modeled as a random effect, the others are all fixed effects.

To explore whether hormonal levels or imaging atrophy patterns predict behavioural response to OXY, we will conduct a linear regression with NPI apathy domain change scores for OXY-PBO as the dependent measure and predictors of regional MRI atrophy ratings (scores from the Harper et al. visual rating scale for each of the following regions: orbitofrontal, rostral anterior cingulate, fronto-insula, medial temporal, and posterior), baseline serum estrogen level (continuous), baseline serum testosterone level (continuous), sex, and treatment order.

The following endpoints are included in the prospective analysis plan:

Table 6.1A. Endpoints for Analysis

#	Endpoint	Role	Endpoint Type	Pop	Model

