1	NPI – Apathy Domain Change Score	Primary Efficacy Endpoint	Continuous Outcome. Higher scores represent worse apathy values.	PPP Most promising dose group (Q3D) from stage 1 and stage 2	$Y_{\text{period}} = \text{Intercept} + \text{subject} + \text{period2} + \text{female} + \text{OXY}$ The intercept covers the reference group of placebo, period #1, and male. The “OXY” is an indicator of treatment – OXY. The Period2 is an indicator of it being the second period. The ‘female’ is an indicator of female patient. Y_{period} represents the NPIA domain score at End of Treatment for that period – score at Baseline for that period
2	NPI – Apathy Domain Change Score	Primary Efficacy Endpoint Supportive Analysis	Continuous Outcome. Higher scores represent worse apathy values.	MITT Most promising dose group (Q3D) from stage 1 and stage 2	$Y_{\text{period}} = \text{Intercept} + \text{period2} + \text{subject} + \text{female} + \text{OXY}$
3	NPI – Apathy Domain Change Score	Primary Endpoint Sensitivity Analysis	Continuous Outcome. Higher scores represent worse apathy values.	PPP – all dose groups combined	$Y_{\text{period}} = \text{Intercept} + \text{period2} + \text{subject} + \text{female} + \text{OXY}$
4	NPI – Apathy Domain Change Score	Primary Efficacy Endpoint Sensitivity Analysis	Continuous Outcome. Higher scores represent worse apathy values.	PPP exclude all new behaviour meds Most promising dose group (Q3D) from stage 1 and stage 2	$Y_{\text{period}} = \text{Intercept} + \text{period2} + \text{subject} + \text{female} + \text{OXY}$
5	NPI – Apathy	Efficacy Endpoint	Continuous Outcome.	PPP	$Y_{\text{period}} = \text{Intercept} + \text{period2} + \text{subject} + \text{female} + \text{OXY}$

	Doman Change Score	SUBGROUP	Higher scores represent worse apathy values.	Most promising dose group (Q3D) from stage 1 and stage 2	BY SEX (M/F)
6	NPI – Apathy Doman Change Score	Efficacy Endpoint SUBGROUP	Continuous Outcome. Higher scores represent worse apathy values.	PPP Most promising dose group (Q3D) from stage 1 and stage 2	$Y_{\text{period}} = \text{Intercept} + \text{period2} + \text{subject} + \text{female} + \text{OXY}$ BY SEVERITY (CDR 0-1 vs 2)
7	NPI – Apathy Doman Change Score	Efficacy Endpoint SUBGROUP	Continuous Outcome. Higher scores represent worse apathy values.	PPP Most promising dose group (Q3D) from stage 1 and stage 2	$Y_{\text{period}} = \text{Intercept} + \text{period2} + \text{subject} + \text{female} + \text{OXY}$ BY AGE (0-65 vs >65)

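### Section 6.2 text adjusts the primary model for treatment order, but Table 6.1A row 1 adjusts for period; in the stated model these differ, and the SAP does not say which governs

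*SAP*

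**What the plan says.** The primary analysis appears in two places in Section 6.2.

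**Text.** The change in NPI apathy is analysed with a "linear model with covariates for sex and order of treatment in the crossover". The covariate list beneath has two entries, sex and "Order of treatment (End of treatment 2: Oxytocin versus End of Treatment 2: Placebo". The second is fixed by which drug a participant received in period 2, so it takes the same value in both of that participant's periods. No period covariate is listed.

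**Table 6.1A, row 1.** The equation contains intercept, subject, period2, female and OXY. The table explains that "The Period2 is an indicator of it being the second period" and that "The intercept covers the reference group of placebo, period #1, and male". Period is in the model and sequence is not.

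Other statements settle the type of model. The response "represents the NPIA domain score at End of Treatment for that period – score at Baseline for that period", so each participant contributes one record per period. On the subject term: "Subject is modeled as a random effect, the others are all fixed effects". The primary test is a "nominal 2.5% one-sided test for the primary outcome of change in NPI" (Section 4.1).

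The SAP neither equates treatment order with period nor says whether the text or the table governs.

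**The concern.** In a two-period crossover, period and sequence do different jobs. Period varies within a person and can be separated from the drug effect within a person. Sequence is constant within a person and explains only differences between people. An analyst who codes the covariate list literally fits a model with no period adjustment; an analyst who codes row 1 fits one that has it.

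At stake is the confirmatory test. If change scores differ systematically between the two periods, the two models can give different estimates, intervals and p-values. The same section applies the primary method to all other outcomes, so they inherit the ambiguity. Two admissible models also leave room for a choice after unblinding, which Section 3.5 is meant to close off by having the SAP finalised while blinded.

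**Working it through.** The SAP states no figure to reproduce here: it refers sample size to the protocol and gives no SD, period effect or sequence split.

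**Inputs from the SAP**
- Planned target-dose total: 20 (Section 4, "Twenty participants per arm will be randomized to each of the three dose arms") + 40 in Stage 2 = 60.
- Primary population: PPP, meaning all visits completed and at least 70% compliance in both periods (Section 4.3). This selection happens after randomisation, so equal sequences are not assured.
- Test: one-sided 2.5%, critical value 1.960.

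**Assumed inputs**
- Within-person SD σ = 2.5 points.
- Period effect π (period 2 minus period 1) of 0, 1 or 2 points in size.
- Splits, oxytocin-first/placebo-first: 30/30 (no losses), and 20/30 and 18/32 (ten of the 60 lost to PPP).

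**Bias.** Let D be a participant's oxytocin-minus-placebo difference in change scores and τ the true effect. The mean of D is τ + π in placebo-first participants and τ − π in oxytocin-first participants. With complete pairs:
- Text model (sequence, no period): the OXY coefficient is the plain mean of D, so its expectation is τ + π × (n placebo-first − n oxytocin-first)/N.
- Row 1 model (period): the OXY coefficient averages the two sequence means, [(τ + π) + (τ − π)]/2 = τ for any split.

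Per 1-point period effect, the text-model bias is:
- 30/30: 0/60 = 0
- 20/30: 10/50 = 0.20
- 18/32: 14/50 = 0.28

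Noise-free fits of both models gave the same values, with 0 for the period model throughout.

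**Standard error, balanced sequences.** Without a period term, the variance of D includes the period effect: 2σ² + π² instead of 2σ² = 12.5.
- π = 1: √(13.5/12.5) = 1.039, so 3.9% too large.
- π = 2: √(16.5/12.5) = 1.149, so 14.9% too large.

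**Type I error.** 40,000 simulated trials per setting, τ = 0, with π signed so that the bias favours oxytocin:

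| Split | Size of π | Text model | Row 1 model |
|---|---|---|---|
| 30/30 | 0 | 2.5% | 2.5% |
| 30/30 | 2 | 1.3% | 2.6% |
| 20/30 | 1 | 5.1% | 2.5% |
| 20/30 | 2 | 7.3% | 2.4% |
| 18/32 | 2 | 12.7% | 2.5% |

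At 30/30 there is no bias, so the sign of π does not matter. With unequal sequences and π of the opposite sign, the bias runs against oxytocin by the same amount.

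**When order would be enough.** If the outcome were D itself, one value per person, a centred order term would adjust for period: the same noise-free fits with D as outcome gave zero bias at every split. Section 6.2 uses D as the outcome only in the exploratory regression on hormone levels and atrophy.

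**The case against.** The strongest reply is that the only written equation is already right. Row 1 is labelled the primary efficacy endpoint and defines its terms, and the same equation with period2 appears in every row from 1 to 54 except row 23. Treatment order in the text may be loose wording for period, perhaps carried over from the difference-score regression. This stands as the likelier intention, and it limits the point to a contradiction to be removed. It does not remove the contradiction, because the covariate list defines order explicitly as which drug was given in period 2.

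Four stronger readings are tempting but not supported.
- *The planned estimate is biased.* It is not if row 1 is followed.
- *Order can never adjust for period.* It can when the outcome is the per-person difference.
- *FTD is progressive, so a period effect is to be expected.* Each response is measured from that period's own baseline over a nominal 42 days (Section 3.6). Steady decline therefore adds the same amount to both change scores and cancels. A period effect needs another cause, such as a larger placebo response or regression to the mean in period 1. The SAP gives no evidence for or against one.
- *Exclusions could leave 60 completers in unequal sequences.* The planned total is 60 and withdrawn participants are not replaced (Section 5.2), so 60 completers means no losses. An imbalance caused by exclusions implies a smaller N, hence the totals of 50 above.

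Randomisation in blocks (Section 3.2) also limits imbalance at allocation, and with balanced sequences the text model errs on the conservative side. Set against the 3-point change cited in Section 6.1, 0.20 points is about 7% (0.20/3).

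**Conclusion.** The contradiction stands and concerns the primary analysis: the text gives sequence without period, the table period without sequence, and for the stated response and random subject effect these are different models. Only the table version adjusts the oxytocin contrast for period in participants with both periods.

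The practical effect is conditional. With no period effect on change scores, both models are unbiased. With a period effect and balanced complete pairs, the point estimates agree, but the text version's SE is too large. With a period effect and unequal sequences, the text version is also biased, in a direction that depends on the sign of the period effect and on which sequence is larger. Every size given rests on an assumed period effect and, apart from balanced sequences, an assumed split; the SE and error-rate figures also rest on the assumed SD of 2.5. This is a correction worth making to the rule for the confirmatory test, not evidence that its result will be wrong.

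**What to change.** In the Section 6.2 text and its covariate list, replace order of treatment with period (second versus first). Add one sentence stating that the Table 6.1A row 1 equation, with subject random, is the primary model. Sequence may be added to that model as a further fixed effect but may not take the place of period. Leave treatment order unchanged in the exploratory regression on oxytocin-minus-placebo differences (text of 6.2 and row 44).

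The cost is SAP wording only: no change to data, design or sample size. It is best done, and dated, before the treatment codes are applied. If the analysis has already been run, the report should say which model was fitted. The statistical price of the period term is small: at 20/30 with no period effect, the simulated SE is 0.508 against 0.498.

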3.2 Randomization

Randomization for stage 1 and 2 will be stratified across the treatment groups listed above according to sex and disease severity (CDR score of 0-1 mild vs. CDR score of 2 moderate). Given the number of centres required for a trial in FTD, the study will not be powered to stratify randomization according to centre. Participants will be randomized using variable block sizes concealed from participating sites. Central randomization will occur with web-based Guide 98 and 21CFR11 compliant technology. Central drug coordinator is responsible for randomization and identification of blinded kit assignment. Site coordinators will be provided with kit receipts to provide to local blinded pharmacy for dispensing of appropriate kit on baseline visit days. Only compounding pharmacy and central drug coordinator have access to kit treatment allocation. Central drug coordinator was sequestered and had no contributions to the study other than ordering and tracking kits, and kit assignment.

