5.1 Eligibility

There were no changes to eligibility criteria from the initiation of participant recruitment to end of study.

1. Diagnosis of probable FTD (behavioural variant FTD, FTD-semantic subtype or FTD-Progressive Nonfluent Aphasia) with supportive brain imaging (centrally rated frontotemporal atrophy score of 2 or greater on brain MRI or CT) or known FTD causing genetic mutation.
2. Current symptoms of social apathy/indifference as measured by NPI apathy/indifference severity subscale score ≥ 2 indicating the presence of moderate to marked levels of apathy/indifference.
3. Study partner who consents to study participation and who cares for/visits the patient daily for at least 3 hours/day and who can administer all trial medications.
4. FTLD-CDR score 0-2.5.
5. MMSE >10 .
6. Stable baseline medications related to cognition or behaviour for ≥ 30 days such as acetylcholinesterase inhibitors, memantine, anti-depressants, antipsychotic agents, other mood stabilizers, benzodiazepines.
7. Written informed consent must be obtained and documented (from the patient or, where jurisdictions allow it, from their substitute decision maker).
8. Participant age at screening between 30 and 80 inclusive.

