8	NPI – Apathy Doman Change Score	Primary Efficacy Endpoint SUBGROUP	Continuous Outcome. Higher scores represent worse apathy values.	PPP Most promising dose group (Q3D) from stage 1 and stage 2	$Y_{\text{period}} = \text{Intercept} + \text{period2} + \text{subject} + \text{female} + \text{OXY}$ OXYTOCIN GENE rs53576 AA vs GG vs AG
9	NPI – Apathy Doman Change Score	Primary Efficacy Endpoint SUBGROUP	Continuous Outcome. Higher scores represent worse apathy values.	PPP Most promising dose group (Q3D) from stage 1 and stage 2	$Y_{\text{period}} = \text{Intercept} + \text{period2} + \text{subject} + \text{female} + \text{OXY}$ By FTD clinical subtype: bvFTD vs. svPPA vs. nfPPA
[P u bl is h D at e] 10	EFER	Secondary Efficacy Endpoint	Categorical	PPP Most promising dose group (Q3D) from stage 1 and stage 2	$Y_{\text{period}} = \text{Intercept} + \text{period2} + \text{subject} + \text{female} + \text{OXY}$
11	EFER	Secondary Efficacy Endpoint Sensitivity	Categorical	PPP All doses combined	$Y_{\text{period}} = \text{Intercept} + \text{period2} + \text{subject} + \text{female} + \text{OXY}$
12	EFER	Secondary Efficacy Endpoint Sensitivity	Categorical	MITT Most promising dose group (Q3D) from stage 1 and stage 2	$Y_{\text{period}} = \text{Intercept} + \text{period2} + \text{subject} + \text{female} + \text{OXY}$

13	IRI – Empathic Concern	Secondary Efficacy Endpoint	Continuous outcome. Higher scores represent better values.	PPP Most promising dose group (Q3D) from stage 1 and stage 2	$Y_{\text{period}} = \text{Intercept} + \text{period2} + \text{subject} + \text{female} + \text{OXY}$
14	IRI – Empathic Concern	Secondary Efficacy Endpoint Sensitivity	Continuous outcome. Higher scores represent better values.	PPP – all doses	$Y_{\text{period}} = \text{Intercept} + \text{period2} + \text{subject} + \text{female} + \text{OXY}$
15	IRI – Empathic Concern	Secondary Efficacy Endpoint Sensitivity	Continuous outcome. Higher scores represent better values.	MITT Most promising dose group (Q3D) from stage 1 and stage 2	$Y_{\text{period}} = \text{Intercept} + \text{period2} + \text{subject} + \text{female} + \text{OXY}$
16	IRI - Total Score	Secondary Efficacy Endpoint	Continuous outcome. Higher scores represent better values.	PPP Most promising dose group (Q3D) from stage 1 and stage 2	$Y_{\text{period}} = \text{Intercept} + \text{period2} + \text{subject} + \text{female} + \text{OXY}$

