	Total Score		from 0,1,2,3,4). Higher scores represent worse outcome		
44	NPI – Apathy Doman Change Score	Exploratory biomarker predictors of response	Continuous Outcome. Higher scores represent worse apathy values.	PPP all dose groups combined	$Y_{\text{period}} = \text{Intercept} + \text{period2} + \text{subject} + \text{female} + \text{OXY}$ Linear regression model: Dependent variable: change in NPI Apathy domain scores during OXY – PLC period. Predictor variables: OXT receptor genotype, serum estrogen (baseline), serum testosterone (baseline), change in CSF_oxy, MRI regional atrophy ratings, age, sex, treatment order. -OXYTOCIN GENE rs2254298 AA vs GG vs AG -MRI atrophy ratings (frontal right, frontal left, temporal right, temporal left, etc.)
45	ACE-III	Exploratory Analysis	Continuous Outcome. Higher scores represent better cognition	PPP Most promising dose group (Q3D) from stage 1 and stage 2	$Y_{\text{period}} = \text{Intercept} + \text{period2} + \text{subject} + \text{female} + \text{OXY}$
46	ACE-III	Exploratory Analysis Supportive	Continuous Outcome. Higher scores represent better cognition	MITT Most promising dose group (Q3D) from stage 1 and stage 2	$Y_{\text{period}} = \text{Intercept} + \text{period2} + \text{subject} + \text{female} + \text{OXY}$
47	ACE-III	Exploratory Analysis	Continuous Outcome. Higher scores represent better cognition	PPP – all dose groups combined	$Y_{\text{period}} = \text{Intercept} + \text{period2} + \text{subject} + \text{female} + \text{OXY}$
48	QTcF interval as measured by ECG	Safety Outcome	Continuous < change	mitT	ECG = $Y_{\text{period}} = \text{Intercept} + \text{period2} + \text{subject} + \text{female} + \text{OXY}$ Y_{period} is QTcF interval as measured by EVG, change from baseline in each period.

49	QTcF interval as measured by ECG	Safety Outcome sensitivity	Continuous < change	miITT removing participants outside of >25 minutes post dose	$Y_{\text{period}} = \text{Intercept} + \text{period2} + \text{subject} + \text{female} + \text{OXY}$ Y_{period} is QTcF interval as measured by ECG, change from baseline in each period.
50	serum sodium level	Safety Outcome	Continuous < change	miITT	$Y_{\text{period}} = \text{Intercept} + \text{period2} + \text{subject} + \text{female} + \text{OXY}$ Y_{period} is serum sodium level, change from baseline in each period.

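### Subgroup analyses at the target dose print no treatment-by-subgroup term, use two conflicting age cuts, and leave the severity groups incompletely defined

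*SAP*

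**What the plan says.** SAP section 6.2 lists five subgroup factors for the NPI apathy change score: sex, severity, age, oxytocin receptor genotype and FTD subtype. Table 6.1A rows 5 to 9 carry them out in the per-protocol population at the target dose, Stages 1 and 2 together. Each row prints the primary model (subject, period, sex and treatment) followed by a label or a list of groups. No row contains a product of treatment and subgroup, and no sentence in 6.2 names an interaction test or a contrast between levels.

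The definitions are:

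- **Age.** The text of 6.2 has "Age (median split : young <67 years; older 67+ years". Row 7 has "BY AGE (0-65 vs >65".
- **Severity.** Row 6 has "BY SEVERITY (CDR 0-1 vs 2". This matches the randomization strata in section 3.2, "CDR score of 0-1 mild vs. CDR score of 2 moderate". Eligibility in section 5.1 is "FTLD-CDR score 0-2.5".
- **Genotype.** Row 8 has "OXYTOCIN GENE rs53576 AA vs GG vs AG".

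Row 44 is a separate exploratory regression of the OXY-minus-placebo difference. Its predictors are receptor genotype, two hormone levels and "change in CSF_oxy, MRI regional atrophy ratings, age, sex, treatment order". It pools the three dose schedules, and its note on genotype reads "OXYTOCIN GENE rs2254298 AA vs GG vs AG".

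**The concern.** A subgroup analysis asks whether the treatment effect differs between kinds of patient. Fitting the primary model within each level, which is the plain reading of these rows though not stated, gives an effect per level and no planned estimate of the difference. A reader is then left to compare p-values, and significance in one level but not in another is not evidence that the effects differ.

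The two definition problems add to this. With two age cuts in the current text, either could be called prespecified after the data are seen. With severity groups that may not cover the eligible range, the analyst would have to decide where some participants belong, or whether they drop out.

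**Working it through.** The SAP gives no power, effect size or SD for the subgroup analyses, so there is no figure of its own to reproduce. The check is a comparison of texts, followed by illustrations under stated assumptions.

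**1. Model in rows 5 to 9.** The treatment term is a single indicator, so the printed model has one treatment effect. Row 5 suggests that the formula was carried over unadapted: fitted separately by sex, the sex term is constant, and the four fixed-effect columns (intercept, period, sex, treatment) have rank 3. With OXY x female added and both sexes in one model, there are five columns of rank 5, so the interaction is estimable.

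**2. Does anything else fill the gap?** Regressing the within-patient OXY-minus-placebo difference on a characteristic is in effect an interaction analysis, so row 44 partly answers the question for age, sex and genotype. It falls short in four ways:

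- it pools all dose schedules;
- it details a different SNP from row 8;
- it has neither severity nor FTD subtype;
- it includes change in CSF oxytocin, which comes from an optional sub-study (section 3.1), so a complete-case fit as printed keeps only participants with CSF data.

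The hormone and atrophy regression in the text of 6.2 includes only sex among the five factors.

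**3. Age.** In completed years, exactly those aged 66 change group. Assuming a median age of 65 or 67 and an SD of 6 to 10, that is about 4-7% of patients, or 2.5 to 4 of 60. If exact age is used, those above 65 and below 67 change group: about 8-13%, or 5 to 8 of 60.

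**4. Severity.** If the grouping score is the eligibility score, values above 1 and below 2, and values above 2 up to 2.5, have no group. If it is a different score, the SAP does not say which one or what values it takes.

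**5. How often separate tests disagree when the effect is the same in everyone.** Assume overall power P. The noncentrality is 1.96 + z(P). A level holding share f of the patients has power P(Z > 1.96 - noncentrality x sqrt(f)). With level powers a and b, the chance of exactly one significant level is a(1-b) + b(1-a).

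For P = 80% and a 50:50 split: noncentrality 1.96 + 0.84 = 2.80; level power 0.508 in each; disagreement 2 x 0.508 x 0.492 = 0.50.

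| Overall power | 50:50 level powers | Disagree | 70:30 level powers | Disagree |
|---|---|---|---|---|
| 50% | 0.283 / 0.283 | 0.41 | 0.374 / 0.188 | 0.42 |
| 80% | 0.508 / 0.508 | 0.50 | 0.650 / 0.335 | 0.55 |
| 90% | 0.630 / 0.630 | 0.47 | 0.774 / 0.427 | 0.54 |

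**6. Number of tests.** There are 2 + 2 + 2 + 3 + 3 = 12 subgroup levels. With no effect anywhere and independent tests, the chance of at least one significant level is 1 - 0.95^12 = 0.46 at two-sided 5%, or 1 - 0.975^12 = 0.26 at one-sided 2.5%. The tests reuse the same patients, which lowers this. In a null simulation (6,000 runs at each of N = 40, 50 and 60; assumed shares sex 50/50, severity 70/30, age 50/50, genotype 45/43/12, subtype 60/20/20) it was 36-38% and 19-20%. Both alphas are shown because the SAP does not state which applies to rows 5 to 9.

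**7. What an interaction test can deliver.** At most 20 + 40 = 60 target-dose participants are planned, before per-protocol exclusions. The SE of the interaction relative to the main effect is sqrt(1/f + 1/(1-f)), which is 2.0 at 50:50. If overall power is 80% and the difference between levels equals the overall effect, the noncentrality is 2.80 / 2 = 1.40 and power is about 29%. Five interaction tests give at least one p < 0.05 in 22-23% of null trials in the same simulation (1 - 0.95^5 = 0.23 if independent).

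**The case against.** The formula in Table 6.1A is boilerplate: row 44 prints it and then specifies something else, and row 5 cannot be fitted separately by sex exactly as printed. So the rows may be underspecified rather than a decision against an interaction test. Subgroup levels contain different patients, so if effects and CIs are reported per level, a reader can subtract them and form an approximate CI. The SAP nowhere says that it will read discordant p-values as differential response. Section 6.1 speaks of polymorphisms in the plural, so two SNPs need not conflict. The CDR point is conditional, since the scores carry different labels and the scale may be defined in the protocol. The magnitudes rest on assumed power and shares, and the age conflict moves few patients.

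Much of this is fair as a limit on the claim. The severity point is a request for definition rather than a proven gap, the percentages are illustrations, the second SNP may be deliberate, and the loss of patients in row 44 depends on a complete-case fit. None of it supplies a prespecified comparison at the target dose. Subtraction by the reader is not a planned estimate, and for severity and FTD subtype no other analysis exists in the SAP. The age contradiction stands whatever the number of patients affected.

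**Conclusion.** The concern holds. As written, the SAP fixes no method for estimating whether response differs between subgroups at the target dose. The age subgroup has two incompatible definitions in current text, and the severity groups do not clearly cover the eligible range. The primary test is untouched, so this is a correction that should be made rather than a threat to the main conclusion.

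The 41-55% disagreement rate assumes an identical effect in all patients, overall power of 50-90% and splits of 50:50 or 70:30. The false-positive rates assume no effect and the shares listed above. None of these assumptions comes from the SAP.

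**What to change.** - For each factor in rows 5 to 9, fit one model to all target-dose participants: Y = intercept + subject (random) + period2 + female + subgroup + OXY + OXY x subgroup. For sex, the subgroup term is female itself.
- Report the interaction estimate with its 95% CI and p-value. Show the effect and CI in each level from the same model, descriptively.
- Label these analyses exploratory, with no multiplicity control and no subgroup claim.
- Use one age cut in both the text of 6.2 and row 7.
- State which CDR score defines severity, assign every eligible value to a group, and reconcile this with the strata in section 3.2.

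The cost is SAP wording and minor code. Interaction estimates will be imprecise (power about 29% in the case worked above), and five tests still produce chance findings, hence the exploratory label. Statements about subgroups will be more cautious.
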